3.1.2 Confidence scores

For each lesion (or for each SIOPEN area in which diffuse disease is noted), the observer (or group of observers for the consensus opinion) will also note a confidence score to measure their certainty of the lesion being malignant, on a 5 point scale from 1 (negative) to 5 (definitively positive). See section 3.1.1 detailing how this data will be provided to the Statistician.

3.1.3 SIOPEN scores

SIOPEN scores will be recorded using standard scoring methods for each of the 12 defined skeletal areas. The SIOPEN scores will be provided to the Statistician via validated listings from the Sponsor. Data will be recorded in the eCRF by the Trial Manager at the Central Imaging Unit and Source Data Verified (SDV'd) by a Sponsor Clinical Research Associate. The Sponsor Clinical Study Manager will perform a data review before the eCRF is locked and listings are provided to the Statistician.

In summary, the following data will be provided to the Statistician for each patient for each imaging modality as calculated by each individual Reviewer and as a consensus:

- SIOPEN score

3.1.4 CURIE scores

CURIE scores will be recorded using standard scoring methods for each of the 9 defined skeletal areas, and for soft tissue. The CURIE scores will be provided to the Statistician via validated listings from the Sponsor. Data will be recorded in the eCRF by the Trial Manager at the Central Imaging Unit and Source Data Verified (SDV'd) by a Sponsor Clinical Research Associate. The Sponsor Clinical Study Manager will perform a data review before the eCRF is locked and listings are provided to the Statistician.

In summary, the following data will be provided to the Statistician for each patient for each imaging modality as calculated by each individual Reviewer and as a consensus:

- CURIE score

3.1.5 Safety and toxicity

Safety variables will be measured in the safety populations as noted in section 2.1.

AE's will be reported and presented as tables of frequency of AE's by body system, by worse severity grade observed and by causality. These will be completed by the Sponsor and will not be provided to the Statistician.

3.1.6 [REDACTED]

[REDACTED]

[REDACTED]

[REDACTED]

3.1.8 [REDACTED]

[REDACTED]

[REDACTED]

[REDACTED]

4 Analysis Methods

4.1 General Principles

All endpoints will be summarised using descriptive statistics. Rates will be summarised using counts and percentages, continuous variables will be summarised using n, mean, standard deviation, median and quartiles. Demographics will be presented for all patients in the safety analysis sets. Total numbers of patients in each analysis set will be given with explanations for any exclusions.

Agreement between the same endpoints measured using different modalities will be reported using descriptive statistics only (summary measures of agreement with 95% confidence intervals, and cross-tabulations or line listings directly comparing two sets of measurements) unless specified below.

Additional data may be summarised by CRUK as required for reporting and will be documented separately in the Clinical Study Report.

4.2 Analysis Methods

4.2.1 Primary endpoint

SIOPEN total numbers of lesions detected on [¹²⁴I]mIBG vs [¹²³I]mIBG will be compared as follows:

In the first stage, a total of at least 9 evaluable patients will be recruited, with a combined total of at least 50 lesions positive on [¹²⁴I]mIBG PET/CT. Initially an exact one-sided binomial test of the null hypothesis: $p \geq 97\%$ will be done using $\alpha = 0.05$. If this is rejected in favour of the alternative hypothesis $p < 97\%$, the study will be stopped early for futility.

If the null hypothesis is accepted, a further one-sided binomial test of the null hypothesis, $p \leq 90\%$ will be done using $\alpha = 0.025$. If this is rejected in favour of the alternative hypothesis $p > 90\%$ then the study may be stopped early for efficacy. If this null hypothesis is not rejected, the study will continue to the second and final stage.

Only if following the interim analysis recruitment is to continue, a second stage will be required and will end when an overall total of at least 33 evaluable patients with at least 100 lesions have been recruited. An exact one-sided binomial test of the null hypothesis, $p \leq 90\%$, will be done using $\alpha = 0.025$. If this is rejected in favour of the alternative hypothesis $p > 90\%$ then the study will be declared a success.

All above tests will be done using the following method: For each patient, the total number of lesions assessed as positive by consensus opinion (with confidence score 4 or 5) on [¹²³I]mIBG planar scintigraphy is referred to as n_{123} , and the total number of lesions assessed as positive by consensus opinion (with confidence score 4 or 5) on [¹²⁴I]mIBG PET/CT is referred to as n_{124} , with the minimum of these two numbers known as n_{\min} . The primary endpoint will be reported by the sum of n_{\min} over all patients, divided by the sum of n_{123} over all patients.

In addition, for each patient the difference and ratios between n_{123} and n_{124} will be calculated and the distribution of these variables will be summarised using the median, upper and lower quartiles. The number and percentage of patients with n_{124}/n_{123} less than 1, equal to 1 and greater than 1 will be reported.

Population to be used: Evaluable population & sensitivity population

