9 ASSESSMENT OF IMAGING TECHNIQUES

9.1 PRIMARY ANALYSIS

Analysis of [¹²⁴I]mIBG PET/CT and [¹²³I]mIBG planar scintigraphy will be performed retrospectively by an agreed number of observers who are experienced in the assessment of neuroblastoma. The observers will perform the analysis separately from each other and will be blinded from the scores of the other observers. An observer will perform their review of each modality for a patient several weeks apart. [¹²³I]mIBG imaging and [¹²⁴I]mIBG PET/CT imaging will be reviewed on a Hermes workstation (Hermes Medical Solutions, Sweden). Observers may perform their assessment of study imaging data in batches throughout the study but will not share their scores until the conditions are met to trigger the interim and final analyses as described in section 12.2.

For each modality, suspected lesions will be judged positive, negative, or equivocal with regard to neuroblastoma involvement by each observer. A final determination of each lesion as positive, negative or equivocal will be established through consensus between all observers:

- Positive – all reviewers consider it positive
- Negative – all reviewers consider it negative
- Equivocal – fewer than all reviewers can agree on whether the lesion is positive or negative

The scores for each modality will be submitted to the statistician at the interim and final analyses to meet the primary endpoint. The percentage of positive findings identified on routine [¹²³I]mIBG planar scintigraphy also identified by the novel [¹²⁴I]mIBG PET/CT will be determined. Recruitment will cease during the interim analysis.

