12 DATA ANALYSIS AND STATISTICAL CONSIDERATIONS

12.1 SAMPLE SIZE

The primary endpoint of the study is the percentage of lesions identified as positive using [¹²³I]mIBG planar scintigraphy which are also identified as positive on [¹²⁴I]mIBG PET/CT. The definition of a positive lesion is described in section 9.1. The aim is to prove that there is more than 90% agreement between the methods, with an expected level of agreement of 97%. Patients are expected to have a median of 3 lesions. Lesions are assumed to be independent within patients for the primary analysis. The following two stage design will be used, where the true proportion of agreement is denoted by P:

In the first stage, a total of at least 9 patients will be recruited, with a combined total of at least 50 lesions positive on [¹²³I]mIBG. Initially an exact one-sided binomial test of the null hypothesis: $P \geq 97\%$ will be done using $\alpha = 0.05$. If this is rejected in favour of the alternative hypothesis $P < 97\%$, the trial will be stopped early for futility. With a total of exactly 50 lesions this will occur if 45 or fewer lesions are also positive on [¹²⁴I]mIBG PET/CT.

If the null hypothesis is accepted, a further one-sided binomial test of the null hypothesis: $P \leq 90\%$ will be done using $\alpha = 0.025$. If this is rejected in favour of the alternative hypothesis $P > 90\%$ then the trial may be stopped early for efficacy. With a total of 50 lesions this will occur only if all 50 lesions are also positive in [¹²⁴I]mIBG PET/CT. If this null hypothesis is not rejected, the trial will continue to the second and final stage.

The second stage will end when an overall total of at least 33 patients with at least 100 lesions have been recruited. An exact one-sided binomial test of the null hypothesis: $P \leq 90\%$ will be done using $\alpha = 0.025$. If this is rejected in favour of the alternative hypothesis $P > 90\%$ then the trial will be declared a success. With a total of 100 lesions this will occur if at least 96 lesions are also positive on [¹²⁴I]mIBG PET/CT.

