Overall this design has 82% power and an alpha of 0.03. If the true percentage of agreement is 97% then there is a 22% chance of stopping early for efficacy, and if the true percentage of agreement of 90% then there is a 57% chance of stopping early for futility. The total sample size of 100 lesions was calculated based on a single stage A'hern design with $p_0 = 0.9$ and $p_1 = 0.97$, and the overall power and alpha has been calculated based on exact binomial probabilities.

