12.2 INTERIM AND FINAL ANALYSIS

The interim analysis will be conducted once both of the following conditions are met:

- At least 50 lesions have been identified on [¹²³I]mIBG planar scintigraphy. These lesions will have been identified as positive by a Nuclear Medicine physician at the investigational site.
- A minimum of 9 evaluable patients have completed the study.

The analysis will be done using all identified lesions from at least 9 patients. Therefore, the total number of lesions is expected to be more than 50. The number of lesions identified on [¹²³I]mIBG planar scintigraphy will be reported to the CSM at the CDD at the time of sponsor authorisation of the supply of the [¹²⁴I]mIBG tracer from the manufacturing organisation to the investigational site. The CSM will communicate to the observers and the statistician when the conditions have been met to trigger the interim analysis.

The interim analysis will assess the primary endpoint by comparison of the number of positive lesions detected on [¹²³I]mIBG planar scintigraphy and [¹²⁴I]mIBG PET/CT in order to compare the two modalities. The imaging data will be analysed and scored separately by an agreed number of observers using the same scoring method as described in Section 9.1 in order to prevent subjective bias. Observers may perform their assessment of study imaging data prior to the interim and final

analyses in batches but will remain blinded to the scores of the other observers until the interim and final analyses are triggered and they meet to perform the consensus reviews. Assessment of the reported safety data will be performed at the interim review and will be considered as part of the decision whether to continue recruitment. The feasibility of recruitment of the required minimum number of patients will also be considered in this decision.

The final analysis will be conducted after one of the following conditions is met:

- The study is terminated early
- The end of trial as defined in Section 11 has been reached.

Following lesion detection the agreed number of experienced observers will also perform a semi-quantitative assessment of [¹²⁴I]mIBG PET/CT scans and [¹²³I]mIBG imaging employing SUVmean and SUVmax. The level of disease involvement will be assessed using the International Society of Paediatric Oncology Europe Neuroblastoma (SIOPEN) scoring method and the Curie scoring method (see Appendix 5).

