12.2.1 Statistical Analysis of Primary Endpoint

The proportion of positive lesions detected by routine [¹²³I]mIBG planar scintigraphy which are also identified as positive using [¹²⁴I]mIBG PET/CT will be calculated. An exact one-sided binomial test of the null hypothesis that this proportion is not more than 90% will be performed, using an alpha of 0.025 to define significance.

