1.2 Clinical Study Objectives and Endpoints

Primary objective	Endpoint
1. To show that [¹²⁴ I]mIBG PET/CT can detect an equal or greater number of neuroblastoma lesions compared to conventional [¹²³ I]mIBG planar scintigraphy.	1. Comparison of the percentage of lesions detected as positive by [¹²³ I]mIBG planar scintigraphy which are also considered positive with [¹²⁴ I]mIBG PET/CT.

Secondary objectives	Endpoints
1. To show that [¹²⁴ I]mIBG PET/CT can detect an equal or greater number of neuroblastoma lesions compared to conventional [¹²³ I]mIBG scintigraphy with 3D imaging by SPECT (single photon emission computerised tomography).	1. Comparison of the percentage of lesions detected as positive by [¹²³ I]mIBG SPECT which are also considered positive with [¹²⁴ I]mIBG PET/CT.
2. Assessing the safety and toxicity profile of a single intravenous administration of [¹²⁴ I]mIBG.	2. Determining the causality of each adverse event to [¹²⁴ I]mIBG and grading

Secondary objectives	Endpoints
	severity according to National Cancer Institute Common Toxicity Criteria for Adverse Events (NCI CTCAE) version 4.02.

Tertiary objectives	Endpoints

[REDACTED]
 
[REDACTED]
 
[REDACTED]
 
[REDACTED]
 
[REDACTED]
 
[REDACTED]
	
[REDACTED]
 
[REDACTED]
 
[REDACTED]
 
[REDACTED]
 
[REDACTED]
 
[REDACTED]

[REDACTED]
 
[REDACTED]
 
[REDACTED]
	
[REDACTED]
 
[REDACTED]
 
[REDACTED]
 
[REDACTED]

[REDACTED]
 
[REDACTED]
 
[REDACTED]
 
[REDACTED]
	
[REDACTED]
 
[REDACTED]
 
[REDACTED]
 
[REDACTED]
 
[REDACTED]

[REDACTED]
 
[REDACTED]
 
[REDACTED]
 
[REDACTED]
 
[REDACTED]
	
[REDACTED]
 
[REDACTED]
 
[REDACTED]
 
[REDACTED]
 
[REDACTED]
 
[REDACTED]

Tertiary objectives	Endpoints

[REDACTED]
 
[REDACTED]
 
[REDACTED]
 
[REDACTED]
 
[REDACTED]
 
[REDACTED]
 
[REDACTED]
 
[REDACTED]
	
[REDACTED]
 
[REDACTED]
 
[REDACTED]
 
[REDACTED]
 
[REDACTED]
 
[REDACTED]

[REDACTED]
 
[REDACTED]
 
[REDACTED]
	
[REDACTED]
 
[REDACTED]
 
[REDACTED]
 
[REDACTED]

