1.4 Number of Subjects

The primary endpoint of the study is the percentage of lesions identified as positive using [¹²³I]mIBG planar scintigraphy which are also identified as positive on [¹²⁴I]mIBG PET/CT. The definition of a positive lesion is described in Section 9.1 of the clinical study protocol. The aim is to prove that there is more than 90 % agreement between the methods, with an expected level of agreement of 97 %. Patients are anticipated to have a median of 3 lesions. Lesions are assumed to be independent within patients for the primary analysis. The following two stage design will be used, where the true proportion of agreement is denoted by p .

In the first stage, a total of at least 9 evaluable patients will be recruited, with a combined total of at least 50 lesions positive on [¹²³I]mIBG PET/CT. Initially an exact one-sided binomial test of the null hypothesis: $p \geq 97\%$ will be done using $\alpha = 0.05$. If this is rejected in favour of the alternative hypothesis $p < 97\%$, the study will be stopped early for futility. With a total of exactly 50 lesions this will occur if 45 or fewer lesions are also positive on [¹²⁴I]mIBG PET/CT.

If the null hypothesis is accepted, a further one-sided binomial test of the null hypothesis, $p \leq 90\%$ will be done using $\alpha = 0.025$. If this is rejected in favour of the alternative hypothesis $p > 90\%$ then the study may be stopped early for efficacy. With a total of 50 lesions this will occur only if all 50 lesions are also positive on [¹²⁴I]mIBG PET/CT. If this null hypothesis is not rejected, the study will continue to the second and final stage.

Only if following the interim analysis recruitment is to continue, a second stage will be required and will end when an overall total of at least 33 evaluable patients with at least 100 lesions have been recruited. An exact one-sided binomial test of the null hypothesis, $p \leq 90\%$, will be done using $\alpha = 0.025$. If this is rejected in favour of the alternative hypothesis $p > 90\%$ then the study will be declared a success. With a total of 100 lesions this will occur if at least 96 lesions are also positive on [¹²⁴I]mIBG PET/CT.

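### SAP 4.2.1 tests the primary endpoint on per-patient minima of unmatched lesion totals, which can equal or overstate the protocol's lesion agreement, and the addendum's move to segments states no formula or pooling

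*Combined protocol and SAP*

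**What the plan says.** The protocol states the endpoint as an overlap in three places.

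- Section 9.1: the percentage of positive findings on routine "planar scintigraphy also identified by the novel [¹²⁴I]mIBG PET/CT will be determined".
- Section 12.1: the percentage of planar-positive lesions "which are also identified as positive on [¹²⁴I]mIBG PET/CT". The 90% null and the 97% expectation are set on this quantity.
- Section 12.2.1: the proportion of planar-positive lesions "which are also identified as positive using [¹²⁴I]mIBG PET/CT will be calculated", tested by an exact one-sided binomial test against 90% at 0.025.

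SAP 1.4 repeats the protocol 12.1 endpoint and adds that "The definition of a positive lesion is described in Section 9.1 of the clinical study protocol".

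SAP 4.2.1 then prescribes one method for all the tests. For each patient, n123 is the number of consensus-positive lesions (score 4 or 5) on planar imaging and n124 is the number on PET/CT, "with the minimum of these two numbers known as" n_min. The endpoint is the sum of n_min over the sum of n123.

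SAP 3.1.1 lists what the statistician receives: counts by segment, totals and confidence-score totals, separately for each modality. No match between lesions is listed. SAP 4.1 allows cross-tabulations and line listings, but only descriptively unless a later section says otherwise.

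The SAP addendum, written after a statistical report review in November 2020, says that the primary analysis will be done by skeletal segment and repeated for soft tissue. It does not say whether n_min is kept, whether minima are taken within a patient's segment or within a segment over all patients, or which single test decides success.

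**The concern.** A share of planar lesions confirmed on PET/CT and a ratio of capped totals answer different questions. If planar imaging shows three lesions and PET/CT shows three different ones, lesion agreement is 0/3 but the SAP scores 3/3.

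This statistic decides futility, early efficacy and final success, and SAP 4.2.2 carries it to the SPECT comparison and the CURIE re-analysis. The error rates in protocol 12.1 ("Overall this design has 82% power and an alpha of 0.03") were derived for a binomial count of lesions, each of which either is or is not confirmed. If PET/CT-only lesions can stand in for missed ones, success can be declared too often when true agreement is only 90%.

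Such lesions are not remote. Protocol 2.6.3 says that current planar and SPECT imaging miss very small foci, and SAP 4.2.1 itself plans to count patients with n124/n123 above 1.

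**Working it through.** **Step 1. The plan's own figures, with lesions matched.** Rule from protocol 12.1: stop for futility at 45/50 or fewer; succeed at 50/50; otherwise succeed at 96/100 or more. With X the confirmed count, binomial:

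- Futility at 90%: P(X ≤ 45 | 50, 0.90) = 0.569 (stated 57%).
- Early efficacy at 97%: 0.97^50 = 0.218 (stated 22%).
- Overall success = P(X1 = 50) + Σ over x = 46 to 49 of P(X1 = x) × P(X2 ≥ 96 − x), where X1 and X2 are the confirmed counts in the two sets of 50 lesions. At 90% this is 0.0266 (stated 0.03). At 97% it is 0.8215 (stated 82%).

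The stated figures reproduce, for the matched count.

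**Step 2. Direction of the difference.** For one patient, let m be the number of one-to-one matched lesions, d the planar lesions missed by PET/CT and u the PET/CT-only lesions. Then n123 = m + d and n124 = m + u, so

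min(n123, n124) = m + min(d, u).

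The excess over the matched count is min(d, u), which is zero or positive. It is zero unless a missed lesion and a PET/CT-only lesion occur in the same patient. The same identity holds within a patient-by-segment cell when matches stay within segments. So the matched count ≤ the sum of patient-by-segment minima ≤ the sum of patient minima.

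**Step 3. Size.** The documents give no PET/CT-only rate, so these inputs are assumptions:

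- True agreement is 90%, and lesions are detected independently.
- PET/CT-only lesions are Poisson with mean 0, 0.5, 1 or 2 per patient. The mean is either the same for every patient or proportional to n123 (mean × n123 ÷ 3.03, since 100/33 = 3.03).
- Planar and PET/CT-only lesions are spread equally over 12 segments (addendum Table 1 lists 12 SIOPEN skeletal segments plus soft tissue), or the whole body is one cell.
- There are two lesion patterns, each with 33 patients, 100 lesions and median 3. Near-equal: 17 patients with 50 lesions, then 16 with 50, at 2 to 4 each. Skewed: 9 patients with 50 lesions (1, 1, 1, 3, 3, 3, 3, 15, 20), then 24 with 50 (13 with 1, 10 with 3, one with 7).

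The distribution of summed minima is built up over patients and put through the rule in Step 1. P(success) at true agreement of 90%:

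| Counting rule | Pattern; PET/CT-only lesions | mean 0 | 0.5 | 1 | 2 |
|---|---|---|---|---|---|
| Matched one-to-one | either | 0.027 | 0.027 | 0.027 | 0.027 |
| Patient-by-segment minima, pooled | either; same mean | 0.027 | about 0.035 | 0.045 | 0.07 |
| Patient-by-segment minima, pooled | skewed; proportional | 0.027 | 0.05 | 0.09 | 0.19 |
| Whole-body minima (SAP 4.2.1) | skewed; same mean | 0.027 | 0.20 | 0.50 | 0.88 |
| Whole-body minima (SAP 4.2.1) | near-equal; same mean | 0.027 | 0.25 | 0.63 | 0.97 |
| Whole-body minima (SAP 4.2.1) | skewed; proportional | 0.027 | 0.49 | 0.83 | 0.98 |

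**Step 4. Why the addendum's pooling matters.** A simulation used 13 equal segments, about 3 lesions per patient, a mean of 1 PET/CT-only lesion per patient and true agreement of 90%. The chance of at least 96/100 was about 0.03 matched, 0.04 with patient-by-segment minima, 0.61 with patient minima and 0.95 with segment minima pooled over patients. The addendum's wording does not choose among the last three.

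**The case against.** The strongest defence is textual. The primary objective is that PET/CT "can detect an equal or greater number of neuroblastoma lesions", and protocol 12.2 says "The interim analysis will assess the primary endpoint by comparison of the number of positive lesions detected". SAP 4.2.1 also reports n124/n123 below, equal to and above 1, so the count result would be visible. This explains where the totals came from. It does not make them the endpoint, because the endpoint and the 90% and 97% hypotheses are worded as an overlap. A numerator capped at n123 cannot show a greater number either.

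Three further points stand. A PET/CT-only lesion does no harm unless it shares a patient or cell with a missed planar lesion, so a reader should not infer that any such lesion spoils the stated alpha. The whole-body figures apply SAP 4.2.1 without the addendum. With minima within patient and segment the inflation is much smaller. The addendum does not state that reading, however. Lastly, the Imaging Review Manual cited in SAP 3.1.1 is not available and may describe matching, but SAP 4.2.1 as written does not use a match.

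A reader might also infer that the direction is unknown, because several planar foci could be read as one PET/CT lesion and lower n124. The one-to-one matched count falls equally in that case: two foci read as one give a matched count of 1 and a minimum of 1. Against one-to-one matching, the minimum never understates.

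**Conclusion.** The point holds and should be fixed. The statistic that decides the trial in SAP 4.2.1 is not the endpoint that the protocol and SAP 1.4 define. It equals one-to-one matched agreement or overstates it, by min(d, u) per patient or cell. The alpha of 0.03 is established only for the matched count (0.027, power 0.82).

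The direction follows from the definitions. The size does not. For assumed means of 0.5, 1 and 2 PET/CT-only lesions per patient, the chance of success at 90% agreement is about 0.035, 0.045 and 0.07 with patient-by-segment minima over 12 equal segments. It is 0.05, 0.09 and 0.19 with skewed counts and proportional extras. With whole-body minima it is 0.20 to 0.49, 0.50 to 0.83 and 0.88 to 0.98. These rest on the assumed rates, lesion patterns, equal segments and independence.

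A reader might infer from the largest figures that this trial's false-positive rate was that high. The documents do not support that: they give no PET/CT-only rate, and the addendum replaces the whole-body analysis with one by segment.

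**What to change.** In SAP 4.2.1, define the endpoint as Σm / Σn123. Here n123 counts consensus planar-positive lesions, and m counts those matched one-to-one to a consensus-positive (score 4 or 5) PET/CT lesion under a same-site rule written before any matching. Do the matching at the consensus meeting, after the separate blinded reads, and add the match to the data list in SAP 3.1.1. Report PET/CT-only lesions and n124 against n123 separately, to serve the count objective.

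For scans already read, the matchers should not see the statistical results, and the report should say that matching followed the report review named in the addendum.

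If matching cannot be recovered, the addendum should state that minima are taken within patient-by-segment cells and pooled into one proportion for one test. It should call this a count comparison that can overstate lesion agreement, and not attach the alpha of 0.03 to it. The segment counts are already supplied under SAP 3.1.1, but cancellation within a segment remains.

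The cost is SAP and addendum wording, one data field and one matching step. No extra scan or reader is needed. Scans already read may have to be reopened, and matching planar foci to PET/CT lesions involves judgement. The reported percentage will be the same or lower.
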